11.9. Efficacy Analyses

All Primary, Secondary and Exploratory endpoints (except CGI) can be considered quantitative continuous data (Interval in type). As such the Change from baseline at and at End of Treatment (Visit 4, Day 28 or earlier in the event of withdrawal) will be derived for each patient and analysed using an Analysis Of Covariance (ANCOVA) model to compare the two treatment groups (IRL790 vs Placebo).

The ANCOVA analysis will allow estimation of the size of treatment effects as well as magnitude of differences between the active treatment and control (IRL790 - Placebo). The dependent variable will be the Change from baseline value and Treatment group the explanatory (independent) variable and fixed factor. A baseline covariate term will be included to ensure minimum variance unbiased estimation.

In view of the small sample size and relatively large number of sites there are insufficient degrees of freedom to include Site as a factor in the model.

Model assumptions will be investigated and a suitable data transformation or non-parametric equivalent model substituted if appropriate.

Actual p-values and 95% confidence intervals for least square mean estimates of the treatment effects and differences from placebo will be presented for these models.

The CGI exploratory endpoint is the only other type of data collected. This qualitative and ordinal categorical variable will be analysed using the Van Elteren non parametric hypothesis test (equivalent to Cochran Mantel-Haenszel test with modified ridits (CMH-row mean scores differ). Statistical significance (p-values) for differences between the two Treatment groups (IRL790, Placebo) will be reported together with the actual response proportions.

11.10.Safety Analyses

Safety evaluations include: Adverse events and Concomitant medications reporting, Complete physical examination, Vital signs, ECG (12 lead) at rest and Clinical safety laboratory tests (clinical chemistry, haematology and coagulation).

Adverse events and concomitant medications are recorded throughout the investigational period with the rest performed at Screening, Day 28 (Visit 4 or at Withdrawal) and Follow-up (5-8 days after Visit 4).

All safety laboratory samples are assayed at the local hospital.

All safety evaluations will be presented as Interval or Categorical data summaries (as appropriate) according to Treatment group and Day of assessment (if appropriate) for the Safety population. No formal statistical analyses will be performed.

11.10.1. Adverse Events

All AEs will be summarised according to TEAE or Baseline Event following classification of the verbatim terms according to the Medical Dictionary for Regulatory Activities (MedDRA) dictionary. The number and percentage of patients for all classified events will be presented according to System organ class (SOC) and Preferred term (PT) by treatment group and overall.

Separate summaries will be presented for all AEs by event frequency of occurrence and also for all AEs according to Seriousness, Severity and Relationship.

If appropriate separate summaries according to IRL790 maximum tolerated dose received may be used to support the findings.

11.10.2. Concomitant Medications

Concomitant medication will be summarised by Anatomical Therapeutic Chemical (ATC) code levels 2 and 4 using the World Health Organisation Drug dictionary (WHODD) with the number and percentage of patients by treatment group and overall.

11.10.3. Physical Examinations

Physical examination results will be categorically summarised as the number and percentage of patients according to body type, treatment group and assessment day.

In addition, Weight additionally measured at Follow up following Screening will be summarised with descriptive statistics for Actual values and Change from Screening by treatment group.

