1.7. Previous Clinical Studies

IRL790 has been investigated in two clinical studies, IRL790C001, a phase I randomised, double-blind, placebo-controlled, cross-over, single ascending dose (SAD) and multiple ascending dose (MAD) study in male healthy volunteers and IRL790C002, a phase 1b study of patients with advanced PD experiencing levodopa induced dyskinesia.

In the SAD part of IRL790C001, subjects were divided into two cohorts. Within each cohort the subjects were randomised to one of four treatment sequences, which included three dose levels of IMP. One of the dose levels was repeated once, taken with a standardised meal, all other doses were taken without food. In each of the six administered dose levels (5, 15, 40, 80, 120mg IRL790), six subjects received active drug and two subjects received matching placebo.

In the MAD part of this study, twenty-three subjects were treated with IMP. In the first cohort, nine subjects received IRL790, 40 mg/day for 10 consecutive days and three subjects received matching placebo. In the second cohort, nine subjects received IRL790, 80 mg/day for 10 consecutive days and three subjects received matching placebo.

Overall, IRL790 was well tolerated when given to healthy male subjects at single doses up to 120 mg and at multiple doses of 80mg per day for 10 days. The maximum tolerated dose was set to 120mg as a single dose and the maximal dose for multiple dosing was set to 80mg per day. Most of the treatment emergent (74%) AEs were of grade 1 intensity while 26% were of grade 2 intensity. The majority of AEs (48%) reported were considered as not related to study treatment while 11% were possibly related and 41% probably related. Overall treatment emergent AEs were mild, transient and possibly CNS related.

In agreement with preclinical findings, the pharmacokinetic evaluation in humans showed dose-linear kinetics with rapid absorption (average $T_{max} \approx 1$ h) and log-linear decline with a plasma half-life around 7h. Urine recovery data confirmed elimination from plasma occurred by a combination of renal excretion (fractional excretion around 35%) and metabolic degradation.

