8.1.3. Physical Examination

A complete physical examination will include assessments of the head, eyes, ears, nose, throat, skin, thyroid, neurological, lungs, cardiovascular, abdomen (liver and spleen), lymph nodes and extremities.

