11.10.4. Vital Signs

For blood pressure and pulse rate, descriptive statistics of Actual values and Change from Screening will be used to summarise by treatment group and assessment day. Categorically classified (Normal/Abnormal) results will also be summarised.

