11.10.5. ECG (12-Lead) At Rest

ECG variables will be summarised according to Actual values and Change from Screening using descriptive statistics and will be presented by treatment group and assessment visit. Categorically classified (Normal/Abnormal) results will also be summarised.

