7.5 Safety Endpoints

7.5.1 Physical Examinations

Physical examination results will be categorically summarised as the number and percentage of patients according to treatment group and assessment day.

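### Physical examination findings are tabulated by visit with no count of new or worsened findings, and no weight is scheduled on treatment

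*Protocol*

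**What the plan says.** **Examination content and timing.** Protocol 8.1.3 states: "A complete physical examination will include assessments of the head, eyes, ears, nose, throat, skin, thyroid, neurological". It goes on to lungs, heart, abdomen, lymph nodes and limbs. The Study Schedule and sections 7.2, 7.7 and 7.8 place the examination at Screening, Visit 4 and Follow-up.

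**Examination summary.** Protocol 11.10.3: "Physical examination results will be categorically summarised as the number and percentage of patients according to body type, treatment group and assessment day". SAP 7.5.1: "Physical examination results will be categorically summarised as the number and percentage of patients according to treatment group and assessment day". The two differ only in that the SAP leaves out 'body type'. Neither document defines that term, which presumably means body system, and neither names the result categories for the examination.

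**Neighbouring safety data.** For blood pressure and pulse (Protocol 11.10.4), "descriptive statistics of Actual values and Change from Screening will be used to summarise by treatment group and assessment day". For the ECG (Protocol 11.10.5), "ECG variables will be summarised according to Actual values and Change from Screening using descriptive statistics", followed by "Categorically classified (Normal/Abnormal) results will also be summarised". Laboratory values also have a change from Screening (Protocol 11.10.6).

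**Weight.** Protocol 11.10.3: "Weight additionally measured at Follow up following Screening will be summarised", including change from Screening by treatment group. SAP 7.5.2 carries the same plan. The Study Schedule lists weight at Screening and at Follow-up; the Visit 4 list in 7.7 does not include it.

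**The concern.** Vital signs, ECG and laboratory tests each have a numeric change from Screening behind any category count. The physical examination has no numeric value, so the count by visit is its only planned summary. That count does not say which patients developed something new.

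This matters more than usual here. Inclusion criteria 3 and 4 (Protocol 4.2) require Parkinson's disease with dyskinesia, so patients may enter with neurological findings. The potential reactions in Protocol 9.2 are mostly in the nervous system and include parkinsonism, tremor and rigidity, that is, worsening of signs that may already be present. Without a split by body system, those signs could also cover a new finding elsewhere.

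Protocol 9.2 also lists oedema. A weight gain from fluid might be present on treatment and gone by Follow-up, and no weight is scheduled in between. Safety and tolerability are a stated secondary objective in the Protocol Synopsis, so these tables are part of the evidence for it.

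**Working it through.** The plan gives no figure of its own on this point. The check is on what the planned tables can show.

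**1. What a count by visit identifies.** In one arm, let S be the number abnormal at Screening, n the number newly abnormal at Visit 4, and r the number who returned to normal. Then

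Visit 4 count = S + n − r.

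The planned table gives S and the Visit 4 count, so it yields n − r but not n. If n = r, the table shows no change whatever the size of n. If r = 0 and nobody drops out, subtracting the Screening row gives n exactly.

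**2. Whether a difference between arms survives.** Inputs: 37 per arm (Protocol 11.2). The documents give no rates, so these are assumptions for illustration: a share b is abnormal at Screening in both arms and stays so, and among the rest a new abnormality occurs in 20% on IRL790 and 5% on placebo.

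Difference between arms at Visit 4 = (1 − b) × (0.20 − 0.05)

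| b | Difference (percentage points) |
|---|---|
| 0% | 15 |
| 10% | 13.5 |
| 50% | 7.5 |
| 90% | 1.5 |
| 100% | 0 |

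In counts at b = 35%:
- Screening, each arm: 37 × 0.35 = 12.95.
- Visit 4, placebo: 37 × (0.35 + 0.65 × 0.05) = 14.2.
- Visit 4, IRL790: 37 × (0.35 + 0.65 × 0.20) = 17.8.
- New findings: 37 × 0.65 × 0.05 = 1.2 on placebo and 37 × 0.65 × 0.20 = 4.8 on IRL790.

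The excess on IRL790 is 37 × 0.65 × 0.15 = 3.6 patients in both displays. The signal is lost completely only in a category where every patient is already abnormal. In such a category a plain normal-to-abnormal shift table is also zero; only a category for worsening would help.

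**3. Effect of dropping the split.** With a split by body system, each system has its own b, and nothing in the documents puts skin, thyroid, lungs or abdomen near 100%. With one overall result per patient, b is the share with any abnormal system, including the neurological one. It can only be equal or higher, so the difference in the table above can only be equal or smaller.

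**4. Weight.** Follow-up is 5 to 8 days after the last dose (Protocol 3.1). Protocol 1.7 reports "log-linear decline with a plasma half-life around 7h".
- 5 days: 5 × 24 / 7 = 120 / 7 = 17.1 half-lives; fraction left 0.5^17.1 ≈ 7 × 10⁻⁶.
- 8 days: 8 × 24 / 7 = 192 / 7 = 27.4 half-lives; fraction left ≈ 6 × 10⁻⁹.

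The only weight after Screening is therefore taken after washout from plasma.

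**The case against.** The strongest reply is that little is lost. Both randomised arms are shown at Screening, Visit 4 and Follow-up, so a drug effect can appear as a difference between arms. Worsening of an existing condition counts as a treatment-emergent adverse event (Protocol 9.1) and is summarised by arm (Protocol 11.10.1, SAP 7.5.5). Individual listings are planned (Protocol 11.1, SAP 4.4). The motor signs most likely to be abnormal at entry are rated by MDS-UPDRS Part III at baseline and Visit 4, with an analysis of change. The generic categorical layout in SAP Table 12.1-1 has columns that could carry body systems. All of this stands and limits the point. What remains is that adverse event capture depends on the investigator's reporting, and that listings leave the reader to derive the change by hand.

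Three stronger readings are tempting, and the documents do not support them:
- *Every patient is abnormal at every visit.* The result categories are undefined, and Normal/Abnormal is named only for vital signs and ECG. The protocol's split also leaves the non-neurological systems free to be normal.
- *Counting by visit hides most of a new effect.* Step 2 gives a ratio of 17.8 / 14.2 = 1.25 at Visit 4 against 4.8 / 1.2 = 4 for new findings. That contrast ignores the Screening row of the same table; the excess is 3.6 patients either way.
- *The ECG and vital-sign plans share the fault.* Their measured values already have a change from Screening, and the Normal/Abnormal counts are an addition to it.

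On weight, half-lives describe drug in plasma. A change built up over 28 days need not reverse within 5 to 8 days, oedema would be reported as an adverse event, and the limbs are examined at Visit 4. The Follow-up value is therefore possibly diluted, but not worthless.

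**Conclusion.** The point holds as a minor weakness in descriptive safety reporting. It does not touch the primary analysis, and no formal safety comparison is planned. Two facts rest on the text alone: new or worsened examination findings are not tabulated, and the only weight after Screening is taken off treatment. Two consequences are conditional. Masking by Parkinson signs requires that the SAP table is built on one overall result per patient. A missed weight effect requires that the change is reversible within days. The documents settle neither, and they give no rates from which to size the loss; the percentages in the working only show how it depends on the share already abnormal at Screening. It would be wrong to conclude that the planned tables cannot show a drug effect. The changes are worth making because they cost so little.

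**What to change.** - **Protocol 11.10.3 and SAP 7.5.1:** replace 'body type' with body system, restore that split in the SAP, and define the result categories. Add a table of patients with a finding that is new or worse than at Screening, by body system and arm, at Visit 4 and at Follow-up.
- **Protocol 11.10.4 to 11.10.5 and SAP 7.5.2 to 7.5.3 (optional):** add Normal/Abnormal shift tables from Screening alongside the planned numeric changes.
- **Study Schedule, Protocol 7.7 and 11.10.3, SAP 7.5.2:** record weight at Visit 4, summarise its change from Screening by arm, and keep the Follow-up value labelled as off-treatment. Where Visit 4 has already passed, only the label can be added.

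The cost is one extra table shell and one weighing at a visit where the examination and vital signs are already done. There is one real condition: examination findings must be recorded so that worsening can be identified, because a bare normal/abnormal tick would not show it in a system already abnormal at Screening.

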11.10.4. Vital Signs

For blood pressure and pulse rate, descriptive statistics of Actual values and Change from Screening will be used to summarise by treatment group and assessment day. Categorically classified (Normal/Abnormal) results will also be summarised.

11.10.5. ECG (12-Lead) At Rest

ECG variables will be summarised according to Actual values and Change from Screening using descriptive statistics and will be presented by treatment group and assessment visit. Categorically classified (Normal/Abnormal) results will also be summarised.

11.10.6. Clinical Laboratory Tests

All haematology, clinical chemistry and coagulation laboratory tests will be summarised using descriptive statistics for Actual values and Change from Screening and presented by treatment group and assessment day for each Hospital site separately (due to assays performed locally).

Additionally the local laboratory normal ranges will be used to classify the results as: High, Normal or Low and categorical summaries presented overall according to treatment group and assessment visit. Pooling across all sites is possible here due to the categorical classification.

12. ETHICS COMMITTEE APPROVAL

The study proposal will be submitted to the Ethics Committee in accordance with the national requirements.

The REC shall give its opinion in writing before the clinical trial commences. The Investigator should provide written reports to the REC annually or more frequently if requested on any changes significantly affecting the conduct of the trial and / or increasing risk to the patients.

13. REGULATORY REQUIREMENTS

The study will be authorised by Medicines and Healthcare products Regulatory Agency (MHRA).

Enrolment of patients will not commence until approval has been received from both the Ethics Committee(s) and Competent Authority.

The study will be conducted in accordance with the Declaration of Helsinki, Good Clinical Practice (GCP) and all other national requirements.

14. INFORMED CONSENT

It is the responsibility of the Investigator or an authorised associate to give each potential study patient adequate verbal and written information before any study specific assessments are performed.

The information will include the objectives and the procedures of the study as well as any risks or inconvenience involved. It will be emphasised that participation in the study is voluntary and that the patient may withdraw from participation at any time and for any reason, without any prejudice. All patients will be given the opportunity to ask questions about the study and will be given sufficient time to consider participation before signing the ICF.

Before performing any study-related procedures the ICF must be signed and personally dated by the patient and by the Investigator. A copy of the Patient Information including the signed ICF will be provided to the patient.

Documentation of the discussion and the date of informed consent must be recorded in the source documentation and in the CRF. The Patient Information sheet and the signed ICF should be filed by the Investigator for possible future audits and/or inspections.

The final approved version of the Patient Information and ICF must not be changed without approval from the Sponsor and the applicable EC.

15. DIRECT ACCESS TO SOURCE DOCUMENTATION / DATA

The Investigator must permit trial-related monitoring, audits, Ethics Committee review or regulatory inspection, providing direct access to source data/documents.

16. STUDY MONITORING AND MANAGEMENT

16.1. Training of study site personnel

Before enrolment of the first study patient a Sponsor representative or delegate will perform a Study Initiation Visit at the study site. The requirements of the Clinical Study Protocol and related documents will be reviewed and discussed and the investigational staff will be trained in any study specific procedures and system(s) utilised.

It is the responsibility of the Investigator to ensure that all personnel involved in the study are fully informed of all relevant aspects of the study and have a detailed knowledge of and training in the procedures that are to be executed by them. Any new information of relevance to the performance of this study must be forwarded to the staff involved in a timely manner.

The Investigator will keep a list of all personnel involved in the study together with their function and study related duties delegated. A Curriculum Vitae will be available for all staff delegated study-specific duties.

16.2. Clinical Monitoring

The study site will be periodically monitored at times agreed on by the Investigator and the Monitor. At the time of each monitoring visit, the function of the Monitor is to:

- provide information and support to the investigational team.
- confirm that facilities and resources remain acceptable.
- confirm that the investigational team is adhering to the Clinical Study Protocol, applicable SOPs, guidelines, manuals and regulatory requirements.
- verify that data are being accurately and timely recorded in the CRFs and that IMP accountability checks are being performed.
- verify that data in the CRF are consistent with the clinical records (SDV).
- verify that the correct informed consent procedure has been adhered to for participating patients.

- ensure that withdrawal of informed consent to the use of the patient’s biological samples will be reported and biological samples are identified and disposed/destroyed accordingly, and that this action is documented and reported to the patient.
- verify that AEs are recorded and reported in a timely manner and according to the Clinical Study Protocol.

When the study has been completed, all queries have been resolved and the database has been locked, the Monitor will perform a close-out visit at the study site.

16.3.Source Data

The primary source documents for this study will be the patient’s medical records and all rating scale CRFs and worksheets used to directly record assessment scores for MMSE, MDS-UPDRS, UDysRS and CGI-C throughout the study. If separate research records are maintained by the investigator(s) both the medical record and the research records should be monitored/audited for the purpose of the study.

A separate source data agreement will be generated at the study site before start of enrolment, specifying the location of the source of derived information appearing in the CRF. This document must be signed by the Principal Investigator and the Monitor to confirm agreement before start of recruitment.

The Investigator should guarantee access to source documents to the Monitor, Competent Authorities and the ECs, as required.

16.4.Study agreements

The Principal Investigator must comply with all the terms, conditions, and obligations of the Clinical Study Agreement (CSA) for this study.

Agreements between Sponsor and the study sites must be in place before any study-related procedures can take place, or patients be enrolled.

16.5.Study time table and end of study

The end of the clinical part of the study is defined as the last visit of the last patient participating in the study.

The study is expected to start in Quarter 4, 2017 and to be completed by Quarter 2, 2018.

17. QUALITY ASSURANCE

Authorised representatives of Sponsor, Competent Authority or EC may perform audits or inspections at the study site, including Source Data Verification (SDV). The purpose of an audit or inspection is to systematically and independently examine all study-related activities and documents, to determine whether these activities were conducted and data were recorded, analysed, and accurately reported according to the Clinical Study Protocol, ICH-GCP guidelines and any applicable regulatory requirements. The Investigator will contact the Sponsor immediately if contacted by a Competent Authority about an inspection at the study site.

